### ***10.1.4 Overall Study Risk Management***

The following measures implemented by Kerastem will minimize the risks associated with patients' participation in clinical studies:

- Kerastem selects personnel (Kerastem employees, agents, licensees, and clinical investigators at the sites) with extensive experience in conducting clinical studies and in performing procedures involved in the protocol including fat harvest and procedures involving the hands
- All examinations, treatment procedures, and interpretation of clinical data generated during the study is directed, overseen and analyzed by an appropriately licensed and credentialed physician who has been trained to the clinical study protocol.
- Kerastem developed the clinical protocol and training programs to ensure that the study personnel at Kerastem and at the clinical sites have a strong knowledge and understanding of the clinical protocol, including patient selection criteria and procedure requirements.
- Kerastem will ensure that the investigators are trained to the procedure requirements in the protocol, and the Instructions for Use for the Celution and Puregraft Systems.
- Kerastem carefully developed patient eligibility criteria for the investigation including clearly defined inclusion and exclusion criteria to ensure that only properly selected patients will be enrolled in the clinical study.
- The protocol is designed so that patient treatment and follow-up procedures will be consistent with those of the clinically established standard of care.

### ***10.1.5 Fat Harvest Risk Analysis***

The risks of standard small volume liposuction in healthy patients are known and are minimal and recovery is usually fast. Following standard liposuction the following effects can be expected:

Common

- Edema and redness of the liposuction areas for a few days
- Moderate contusion of the liposuction areas for a few months
- Uncommon
- Persistent edema

- Persistent bleeding
- Hematoma
- Visible puncture sites

Rare

- Infection
- Deep Vein thrombosis (DVT)
- Persistent bleeding requiring transfusion

#### **10.1.6 Fat Harvest Risk Management**

The Investigators and all study personnel will be trained in the details of all aspects of the study procedures. Standardization of fat harvest techniques is critical to a good clinical outcome. To minimize risks and increase the chances of a favorable clinical outcome the following measures are required for the liposuction procedure:

- Performed by an appropriately licensed and credentialed physician
- Monitoring of vital signs throughout the procedure.
- Sterile technique is followed throughout.
- The adipose tissue is handled gently at all times.
- HGB, HCT prior to and 1-2 hours post-procedure
- To sufficiently induce local vasoconstriction/hemostasis during the fat harvest procedure, a minimum of 500 mL of tumescent fluid is used containing:
  - o 500 mL of Lactated Ringers solution
  - o 20 mL of 1% Lidocaine
  - o 1 mg of epinephrine
- A blunt 14 to 16 gauge LAMIS infiltrator (or equivalent) will be used for infiltration with tumescent solution
- After ~10 minutes, the adipose tissue may be harvested through the same incision, using the aspiration cannula attached to a syringe
- A blunt cannula with a minimum inner diameter of 3 mm is preferred for lipoaspiration.
- Lipoaspiration is recommended to be done manually using a syringe (60 mL Toomey syringe is preferred).
- Enrollment of only patients who qualify per the inclusion / exclusion criteria defined in the protocol) including screening blood work
- Strict adherence to the study protocol
- Standard of care for the monitoring of and treatment who experience any adverse event for liposuction
- Target volume of adipose tissue is limited to approximately 450 mL
- Close surgical incision with appropriate suture
- Apply pressure bandage immediately upon conclusion of tissue harvest

Fat harvest should NOT be performed on patients who have received any anticoagulant within 1 hour of the procedure, substantial anticoagulation (e.g.: GIIb/IIIa inhibitor class drugs) within two weeks prior to fat harvest, or who have an abnormal PTT.

## **10.2 Potential Benefits**

This clinical investigation is designed as a safety and efficacy study. Therefore, it is not known at this time whether any direct subject benefit can be expected. Given the proposed mechanism of action of autologous adipose enriched with or without ADRCs, we expect there may also be a beneficial effect in the treatment of baldness due to alopecia androgenetica. Previous ex-US patient experience with similar inclusion/exclusion criteria documented encouraging positive efficacy results and a favorable benefit to risk profile (abstract accepted at 2014 International Federation of Adipose Therapeutics and Science (IFATS) Annual Meeting-November 2014).

## **11 STATISTICAL METHODS AND DATA ANALYSIS**

This is a multi-centre, single-blinded, randomized, parallel group, controlled study to evaluate the preliminary safety of cell-enriched autologous fat compared to placebo in patients with baldness due to alopecia androgenetica. The primary endpoint will be the safety and tolerability of the procedure.

An analysis of covariance (ANCOVA), with the baseline measure used as a covariate, will be used for the analyses of the secondary efficacy endpoints. Comparisons of each active arm with placebo will be made using Dunnett comparisons. The ITT population will be used for the primary analysis; the analysis will also be performed in the PTE population and will be considered as supportive of the ITT analysis.

### **11.1 General Considerations**

All statistical tests will be two sided, and statistical significance will be assessed with respect to a nominal p-value of 0.05. Before the first data review meeting of the DMC is held, a separate statistical analysis plan (SAP) will be completed, providing detailed methods for the analyses outlined in the following subsections. The SAP will detail all planned analyses and will serve as a statistical programming requirements document.

### **11.2 Determination of Sample Size**

The sample size for the trial has been set at 70, based on clinical considerations and is not based on formal power calculations.

The objective of the STYLE Trial is to assess the safety and preliminary efficacy of cell-enriched autologous adipose delivered via a subcutaneous route in the treatment of baldness due to alopecia androgenetica. As the primary endpoint is safety and tolerability, the investigators believe that a sample of 20 subjects per arm and a 10 patient no-fat saline control is adequate.

### **11.3 Data Analyses**

Safety and efficacy endpoints will be summarized by treatment group using descriptive statistics (n, mean, SD, median, minimum, and maximum), for quantitative variables and frequencies and percentages for categorical variables. Laboratory data will also be summarized using shift tables

between before procedure and at Day 1, post procedure, with values categorized as less than lower limit of normal range, within normal range, and above upper limit of normal range.

For quantitative efficacy variables, summaries will be provided at each post-baseline visit time point. Additionally variables will be analyzed using ANCOVA models with adjustment for the baseline value of the variable.

Related adverse events will be analyzed separately for those related to ADRCs and the delivery of ADRCs (i.e., injection site such as shock loss). A separate safety analysis will be performed for Adverse Events of Interest ([Appendix B, Adverse Event Terminology and Grading](#)).

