## Summary of Changes Document – Clinical Protocol

---

In November 2015 the STYLE Clinical Trial Protocol—Rev A, August 21, 2015 was modified to Rev B, November 24, 2015. This document highlights the changes that were made in the revision.

1. **Blinding (Section 5.3):** we adjusted the document to accurately reflect which parties are blinded and unblinded in carrying out the protocol. Given that a no-fat control is currently a group within the study and it is unfeasible to disguise this treatment relative to a fat containing arm, the sponsor, data management personnel (CRO), and study monitors will be aware of which treatment the subject received. It is imperative to note that the above parties have no potential impact in either the outcome or risk profile as core analysis (e.g., global and macrophotography) will remain conducted by blinded observers. It should also be noted that the statistician working to analyze the data will also remain blinded.
2. **Questionnaires (Sections 8, 9.6, & Appendix A):** we adjusted the protocol to remove inconsistencies with the timing of both investigator and subject questionnaires. Both of these questionnaires (attached in the correspondence) are not relevant for any pre-procedure assessment as they reflect perceived changes subsequent to the intervention. As such, the sections of the document reflecting this timing have been amended accordingly. This change has no potential impact in either the outcome assessment or risk profile of the protocol.
3. **Timing of visit (Sections 9.1 & Appendix A):** the original protocol called for acquisition of both global and macrophotography at Day -1. In the course of working with the approved vendor (Canfield Scientific), it became evident that this time period would not allow adequate time to monitor for the quality of the images obtained. As such, we are proposing that both global and macro photography is acquired at least one month and no later than one week prior to the scheduled intervention to allow for this critical quality assessment. With this change, we are eliminating one round of global photography. This change has no potential impact in either the outcome assessment or risk profile of the protocol.

Subcutaneous Transplantation of Autologous Cell Enriched Adipose  
Tissue For Follicular Niche Stimulation in EarLY Stage ALopecia  
Androgenetica (STYLE): a Randomized, Blinded, Controlled Trial

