### **5.3 Blinding Procedures and Safeguards**

The following will be the “blinded parties”, meaning that the listed will have no knowledge of the patient’s treatment assignment:

- Patients
- Core Laboratories
- Statistician

The “**unblinded parties**”, meaning those that will or may have knowledge of a patient’s treatment assignment, will be the following:-

- Investigators
- Unblinded Pharmacist or designee involved in the dose preparation procedures and randomization of the patient
- Data Monitoring Committee Members

The study blind should not be broken except in a medical emergency (where knowledge of the test material received would affect the treatment of the emergency) or regulatory requirement (e.g., for SAEs or death).

If unblinding becomes necessary, the Investigator should notify the Sponsor or the Medical Monitor as soon as possible. If the blind is broken, the date, time and reason must be recorded in the Subject’s electronic case report form (eCRF), together with a note of a protocol violation if applicable, and any applicable reports [e.g. Adverse Event (AE)].

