## **12.2 Procedures for AE Reporting**

All AEs will be recorded by the investigator or designee on the appropriate electronic case report form (eCRF). Events that occur prior to the liposuction-related activities, including those that are considered serious, are to be recorded in the medical history. Events, including SAEs, which occur after liposuction-related activities are initiated on procedure day, are to be recorded on the AE eCRF. The investigator will evaluate the relationship of the adverse event to both the test material and study procedure as unrelated, unlikely, possibly, probably, or definitely related and will record the findings, including all pertinent details of the event on the eCRF.

In addition, the Investigator or designee will report any serious adverse events, including UADE, occurring during this study to the Sponsor and Medical Monitor as soon as possible, but no later than 24 hours after the Investigator first identifies the adverse event.

The Investigator will take appropriate measures to ensure the subject's well-being and document these measures on the appropriate eCRF.

All serious adverse events experienced will be monitored until the event has resolved, any abnormal laboratory values have returned to baseline or stabilized at a level acceptable to the Investigator and Medical Monitor, or until there is a satisfactory explanation for the changes observed.

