## APPENDIX A: SCHEDULE OF PROCEDURES

	Pre-procedure Assessment	Procedure Day		Post-Operative Follow-up Week				52 ± 2 wks
		Day -1	Day 1	1 ± 1 day	6 ± 3 days	12 ± 1 wk	24 ± 2 wks	
Informed consent	X							
Confirm Inclusion / Exclusion criteria	X	X						
Medical history including Demographics	X	X 						
Physical examination	X	X	X	X	X	X	X	X
Vital signs	X	X	X 	X	X	X	X	X
Laboratory tests	X	X	X					
Pregnancy test 	X	X	X					
Injection assessment	X							
Global Photography	X				X	X	X	X
Trichogram capture	X				X	X	X	X
Investigator Hair Satisfaction Questionnaire					X	X	X	X
Subject Hair Satisfaction Questionnaire					X	X	X	X
Randomization			X					
Sterility Testing			X					
Injection Procedure			X					
Adverse Events			X	X	X	X	X	X

. Adverse Events that occur prior to the liposuction-related activities, including those that are considered serious, are to be recorded in the medical history.

. Vital signs will be monitored according to institutional procedures; it is suggested that vitals be monitored frequently during the fat harvest, between fat harvest and cell injection and during cell injection procedure and for at least one hour following the injection procedure

. Women of child-bearing potential

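### Shock loss is a named injection harm, yet no planned safety analysis counts by arm the subjects whose trichogram density fell

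*Combined protocol and SAP*

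**What the plan says.** All references are to protocol Rev B unless stated.

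- **The harm.** Section 10.1.1 lists shock loss among the risks of subcutaneous delivery. Section 11.3 plans a separate analysis of related events, split into "those related to ADRCs and the delivery of ADRCs (i.e., injection site such as shock loss". It also plans an analysis of events of interest taken from Appendix B, but Appendix B has no shock-loss row or grade.
- **Who reports it.** Section 12.2: "All AEs will be recorded by the investigator or designee on the appropriate electronic case report form (eCRF"), and "The investigator will evaluate the relationship of the adverse event to both the test material and study procedure". Section 5.3 puts investigators first among the unblinded parties, "meaning those that will or may have knowledge of a patient"'s assignment.
- **The other safety route.** Section 11.3.1 includes physical-examination abnormalities to Week 24 in the primary safety evaluation. The body systems in Section 8.1 include head and skin. Scalp hair is not named, and neither is a blinded examiner.
- **The measurement.** The Appendix A row "Trichogram capture" is marked before the procedure and at Weeks 6, 12, 24 and 52. Section 5.3 lists "Core Laboratories" as blinded, and the Summary of Changes says that "core analysis (e.g., global and macrophotography) will remain conducted by blinded observers".
- **Its planned use.** Density at Week 24 is a secondary efficacy endpoint, defined as change from baseline (4.5.2). Density at other weeks is exploratory (4.5.3). Section 11.3 gives the mean, SD, median, minimum and maximum by arm, with efficacy summaries at each post-baseline visit. It continues: "Additionally variables will be analyzed using ANCOVA models with adjustment for the baseline value of the variable".

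**The concern.** The primary endpoint is safety and tolerability to 24 weeks, and hair lost because of a hair-loss treatment is a central harm. The trial schedules an objective measure of hair density three times after baseline within that window, with core laboratories on the blinded list. No part of the plan uses a fall in density as a safety outcome or compares it with the event reports.

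In people who already have alopecia, deciding whether hair loss is an adverse event, and whether the injection caused it, takes judgement. An event attributed to the underlying condition would not enter the analysis of related events. That judgement is made by staff who may know the arm. A between-arm comparison of shock loss therefore rests on the source most open to assessor bias, while a less exposed source is reported under another heading and in a form that gives no count of affected subjects.

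**Working it through.** **1. Sources set side by side**

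| Source | Role in plan | Assessor blinded? | Count of subjects with hair loss by arm? |
|---|---|---|---|
| Adverse events | Safety | Investigators listed as unblinded | Yes, if reported; no definition or grade |
| Physical examination | Safety | No blinded examiner named | No hair-loss criterion |
| Trichogram density | Efficacy only | Core laboratories listed as blinded | No |

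**2. Inputs.** The allocation reproduces: 70 × 2/7 = 20 for three arms and 70 × 1/7 = 10 for the no-fat arm. Section 11.2 says the total has no power basis. The documents give no shock-loss rate, density SD or decline limit, so the values in steps 3 to 5 are assumptions.

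**3. What the planned descriptives show.** If k of 20 subjects lose L% and the others gain g%, the mean change is (−kL + (20 − k)g)/20.

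- k = 2, L = 30: g = 0 gives −60/20 = −3.0; g = 5 gives (−60 + 90)/20 = +1.5; g = 10 gives (−60 + 180)/20 = +6.0.
- With L = 30 and g = 5, the mean is +3.25, +1.5 and −2.0 for k = 1, 2 and 4. In all three cases the median is +5 and the minimum is −30.

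The median and minimum are the same whether one, two or four subjects lost 30%. The mean and SD do move, but with ordinary spread they cannot be turned back into a count. In addition, Section 4.5.3 does not say change from baseline for Weeks 6 and 12. If raw density is summarised there, the minimum is the sparsest scalp, not the largest loss.

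**4. ANCOVA as a check for this harm.** Take the 3-point shift above (k = 2, L = 30, the other 18 behaving like controls). Compare 20 with 20, two-sided at 0.05, using a noncentral t with 38 df and noncentrality 3/(SD × √(2/20)).

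| Assumed SD (points) | Noncentrality | Power |
|---|---|---|
| 10 | 0.949 | 15% |
| 15 | 0.632 | 10% |
| 20 | 0.474 | 8% |

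Over 2 to 4 losers, losses of 20 to 40% and SDs of 10 to 20, power runs from 6% to 69%. The Dunnett adjustment in Section 11 is not included and would lower it.

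**5. Event reports.** At a true rate of 10%, the 40 ADRC subjects give 40 × 0.10 = 4 expected cases. If half are reported, 2 are expected. The chance of at least one report in an arm of 20 falls from 1 − 0.90²⁰ = 88% to 1 − 0.95²⁰ = 64%.

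**6. What a per-subject count could say.** Exact 95% intervals:

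| Count | Interval |
|---|---|
| 0/20 | 0 to 16.8% (upper limit 1 − 0.025^(1/20)) |
| 2/20 | 1.2 to 31.7% |
| 4/20 | 5.7 to 43.7% |
| 0/40 (ADRC arms pooled) | 0 to 8.8% |
| 0/10 | 0 to 30.8% |

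Fisher's exact test gives p = 0.106 for 4/20 against 0/20 and p = 0.047 for 5/20 against 0/20. The table describes; it does not test.

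**The case against.** The case against is substantial, and much of it stands.

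- **Density is not reduced to a mean.** A reader might infer that it is. Section 11.3 plans the median, minimum and maximum too, at each visit, so a large individual loss in change from baseline would show as the minimum. What those figures lack is the number of subjects affected.
- **Adverse events are not the only route.** Physical-examination abnormalities are part of the primary safety evaluation. Global photographs are read by blinded observers, and subjects are blinded and complete a questionnaire, although neither source is a designated safety outcome.
- **A zero or positive mean does not imply that the ANCOVA shows no harm.** The planned comparison is with placebo, so nothing follows until a control mean is assumed. Step 4 claims only low power over part of an assumed range.
- **The documents do not say that a trichogram at Week 6 or 12 would show shock loss.** They neither define it nor say when it appears. They do not place the tattooed site relative to the 40 cm² treated area. Detailed instructions are in the Study Reference Manual, which is not in the file.
- **Investigators may not always know the arm.** Section 5.3 says will or may, and the fat-alone second injection is visually matched to ADRCs. They are still on the unblinded list.
- **A separate SAP is promised in Section 11.1 and is not in the file.** It could contain this table. The point concerns the plan as it stands, and the SAP is the natural place for the addition.
- **A cut-off applied at any of three visits will flag some measurement error.** True; this is why the limit should come from repeatability data and the control arms should be shown alongside.

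**Conclusion.** The point holds as a gap in the safety analysis that is cheap to close. Shock loss is a named harm, its safety capture depends mainly on investigators listed as unblinded, and it has no definition or grade in Appendix B. The density data, with core laboratories listed as blinded, are planned only as efficacy and in a form that does not count affected subjects.

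The documents do not support saying that the harm would go unseen or that the trial is biased as a result. The gain is a between-arm view less exposed to assessor knowledge, with wide intervals: no cases among 20 leaves rates up to 16.8% open.

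The conclusion rests on three assumptions: the trichogram site lies within the treated area, shock loss is visible at Week 6, 12 or 24, and the blinded core laboratories read the trichograms. The loss sizes, SDs and reporting shares in the working are illustrations.

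**What to change.** 1. **Add a safety table to Section 11.3 or the SAP.** By arm, give the number and percent of treated subjects whose trichogram density is below baseline by more than a fixed limit at Week 6, 12 or 24, with exact 95% intervals. Fix the limit before unblinding, preferably at the core laboratory's repeatability limit; 10% and 20% are only examples. Use observed values, since Section 11.6 does not impute safety data, and show how many subjects have no usable reading.
2. **Add a plot of individual change by arm.** Read it and the table beside the shock-loss events and against the control arms. Both control arms also receive scalp injections (Section 7.2), so report the proportion in each arm as well as the contrasts.
3. **Define shock loss for recording** and give it a row in Appendix B.
4. **State the assumptions** on site position, timing and who reads the trichograms, and have the sponsor confirm them.
5. **Reconcile Section 9.6 with Appendix A.** The Section 9.6 test list omits the trichogram that Appendix A schedules at the same visits.

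The cost is one table and one figure from measurements already scheduled, plus a short definition. The drawback is that a cut-off must be chosen in advance, some declines will be measurement error, and the result is descriptive only. No dose or treatment rule changes.

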### ***11.3.1 Primary Endpoint Analysis***

The primary endpoint for the study is safety and tolerability through 24 weeks

The hypotheses are:

Adverse event rates through 24 weeks for active treatment will be less than or equal to adverse events rates published for autologous fat grafting.

Vital sign abnormalities through 24 weeks for active treatment will be less than or equal to those published for autologous fat grafting.

Physical exam abnormalities through 24 weeks for active treatment will be less than or equal to those published for autologous fat grafting.

The corresponding null hypotheses are that the adverse event rates will be greater for active treatment arms than for placebo.

Statistical testing will not be performed for these hypotheses, but the safety endpoints will be evaluated clinically.

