### **7.2.1 Justification of Control Dose**

To reduce the risk of bias (selection bias, performance bias, detection bias and attrition bias), all patients will undergo pre-specified screening procedures, fat harvest, and injection of active treatment or placebo. The justification and rationale of the placebo dose arm include:

1. In the presence of a concurrent placebo control group, demographics and patient selection is more likely to be balanced allowing for more reliable interpretation of study results.
2. Minimize the potential of the Hawthorne effect creating a positive impression of efficacy that may overstate the actual treatment effect.

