## **12 ADVERSE EVENTS / SERIOUS ADVERSE EVENTS**

### **12.1 Definitions**

An **adverse event (AE)** is defined as any undesirable experience occurring to a Subject during the course of the study, whether or not it is related to the test material or the study procedure. Expected adverse events are those that are listed as known risks of the liposuction or injection procedure including those described in this protocol, informed consent, and/or the Investigator's Brochure.

A **serious adverse event (SAE)** is defined as any untoward medical occurrence that:

- Results in death,
- Is life-threatening,
- Requires or prolongs Subject hospitalization
- Results in persistent or significant disability or incapacity
- Is an important medical event(s) that may not be immediately life-threatening or result in death or hospitalization but that may jeopardize the Subject or require intervention to prevent one of the above outcomes
- Is a congenital anomaly/birth defect.

Medical and scientific judgment should be exercised in deciding whether a case is serious and whether expedited reporting is appropriate.

An **Unanticipated Adverse Device Effect** is defined as any serious adverse effect on the health and safety or any life-threatening problem or death caused by, or associated with the Celution or Puregraft system devices, if that effect, problem, or death was not previously identified in nature, severity, or degree of incidence in the investigational plan or application or any other unanticipated serious problem with the Celution or Puregraft system devices that relates to the rights, safety or welfare of subjects.

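### The three primary safety hypotheses rest on unsourced published fat-grafting rates, and the null on an undefined placebo, when a randomized fat-alone arm with the same procedures and visits could be the reference

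*Combined protocol and SAP*

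**What the plan says.** Section 11.3.1 (same text in Rev A and Rev B) sets out three hypotheses for the primary endpoint, safety and tolerability through 24 weeks. The first reads "Adverse event rates through 24 weeks for active treatment will be less than or equal to adverse events rates published for autologous fat grafting". The second and third repeat that comparator, one for abnormal vital signs and one for abnormal findings on physical examination.

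The section gives no published figure, source, event definition, grading scale or follow-up period. Its null sentence changes the comparator and covers one of the three outcomes: "The corresponding null hypotheses are that the adverse event rates will be greater for active treatment arms than for placebo". Which control arm is meant is left open. The section closes by stating that the hypotheses will not be tested and that safety will be judged clinically.

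Other sections fix what the trial counts. Section 12.1 defines an adverse event as "any undesirable experience occurring to a Subject during the course of the study, whether or not it is related to the test material"; no link to the harvest or injection is needed either. Sections 8.5 and 12.2 start recording once the procedure begins on Day 1. Sections 9.5 and 9.6 and Appendix A schedule assessments at Weeks 1, 6, 12, 24 and 52. Section 10.1.5 introduces its list of edema, redness and contusion with "Following standard liposuction the following effects can be expected", and Appendix B grades localized bruising and mild pain.

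On comparators, Section 5.2 randomizes 20 subjects to fat alone. They have the same harvest, two scalp injections and the same visit schedule as the active arms. Section 7.2.1 argues that "In the presence of a concurrent placebo control group, demographics and patient selection is more likely to be balanced", and Section 11 describes the aim as to "evaluate the preliminary safety of cell-enriched autologous fat compared to placebo in patients". Section 11.3 plans safety summaries by treatment group, a separate analysis of events related to the ADRCs and their delivery, and another of the Appendix B events.

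**The concern.** The two sides of the stated comparison are not shown to measure the same thing. The trial side counts any event from any cause, including the after-effects of a liposuction that every subject undergoes, and asks about events at fixed visits. The literature side is unspecified. Nothing requires its events, window, grading or visit frequency to match. The fat-grafting sources cited in Section 2 are mainly breast and body-contouring work, with no scalp series.

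If the trial collects more than the literature did, a harmless product can look worse than published. If the benchmark comes from a setting with higher background rates, a harmful product can look acceptable.

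A reference free of this mismatch is already being paid for. Effects of harvest and injection that are shared with the fat-alone arm cancel in expectation, leaving the contribution of the ADRCs. The hypotheses do not use that arm, and the null sentence points to a comparator that could be fat alone, no fat, or both.

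**Working it through.** **Inputs from the documents.** Arm sizes 20, 20, 20 and 10 (Section 5.2), so 40 pooled active and 20 fat-alone. The allocation reproduces: 70 × 2/7 = 20 and 70 × 1/7 = 10. There is no benchmark rate, margin or power figure to reproduce.

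**Assumptions (not in the documents).** Published rate b; share L of subjects with a donor-site event that the published rate does not count; independence between donor-site and graft events; no ADRC effect unless stated.

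**1. Trial collects more than the literature.** Any-event rate q = 1 − (1 − b)(1 − L). The probability that the observed active rate exceeds b is P(X > 40b) with X ~ Binomial(40, q).

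| b | L | q | P(observed > b) |
|---|---|---|---|
| 10% | 0 | 10% | 0.37 |
| 10% | 10% | 1 − 0.9 × 0.9 = 19% | 0.90 |
| 10% | 30% | 1 − 0.9 × 0.7 = 37% | >0.99 |
| 20% | 0 | 20% | 0.41 |
| 20% | 10% | 1 − 0.8 × 0.9 = 28% | 0.83 |

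The L = 0 rows are the baseline. With perfectly matched collection the observed rate still exceeds the benchmark about four times in ten by chance. They also describe the case where published rates already include harvest events: the spurious excess is then zero.

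**2. Benchmark set in a higher-rate setting.** Suppose ADRCs double the rate from 10% (fat alone) to 20%, and the published rate is 30%. The hypothesis appears met when X ≤ 12 of 40 with X ~ Binomial(40, 0.20): probability 0.96. For 20% doubled to 40% against a published 50%, P(X ≤ 20) = 0.93.

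**3. Fat-alone arm as reference.** With no ADRC effect and a common collected rate, the probability that the pooled active rate is above the fat-alone rate stays between 0.44 and 0.47 for collected rates from 5% to 60%. It barely depends on how intensively events are sought.

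**4. Precision of that comparison.** 95% half-width = 1.96 × √[p(1 − p)(1/n₁ + 1/n₂)], with the same rate p in both arms.

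| p | 40 v 20 | 20 v 20 |
|---|---|---|
| 20% | 21 points | 25 points |
| 37% | 26 points | 30 points |
| 55% | 27 points | 31 points |

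Power at two-sided 0.05 for 40 v 20 is 33% for 20% against 40%, and 62% for 20% against 50%.

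**5. Dilution in an all-cause count.** With L = 50%, doubling graft-related events from 10% to 20% moves the any-event rate only from 1 − 0.9 × 0.5 = 55% to 1 − 0.8 × 0.5 = 60%. An all-cause difference alone could hide harm, so the related and Appendix B events need the same contrast.

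**The case against.** The strongest reply is that nothing is formally decided by the benchmark. Section 11.3.1 rules out testing and sets no threshold, so the event that the observed rate exceeds the published rate triggers nothing. That stands. A reader might infer that event collection will determine whether the trial meets its primary endpoint, but there is no such rule for it to determine.

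Second, concurrent information is partly planned: the null names placebo, Section 11 frames safety against placebo, Section 11.3 tabulates safety by arm, and events related to the ADRCs or their delivery are analyzed separately. This also stands, and it means a clinical evaluator will see the fat-alone data and can set aside many expected liposuction effects. It does not supply an active-minus-fat-alone contrast, and it leaves hypothesis and null on different comparators.

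Third, the sources may count harvest events. Section 2.1 describes fat transfer as including aspiration from a donor site. A reader might infer a spurious excess of 9 points (19% − 10%) or more as a finding about this trial. The documents do not support that, because neither b nor L is given, and Section 10.1.5 says common without a rate.

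Fourth, a separate SAP is promised in Section 11.1 and could define the benchmark. It is not among these documents, and the hypotheses sit in the protocol.

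Fifth, a reader might infer that the fat-alone arm removes all bias. It does not: Section 5.3 lists investigators as unblinded, and under Section 12.2 they record events and rate relatedness. The arm equalizes procedures and schedule, not assessment.

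**Conclusion.** The concern holds as a defect in the stated basis of the primary safety conclusion. All three hypotheses point to an unsourced external benchmark, the null points to an undefined concurrent one, and the arm that isolates the ADRC contribution is not named.

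The size can only be illustrated. Under the assumptions above, uncounted donor-site events in 10% of subjects raise the chance of exceeding a 10% benchmark from 37% to 90%; an overly high benchmark lets a doubling of risk pass with probability 0.96. Both depend on rates that the documents do not give, and the first disappears if published rates include harvest events. The vital-sign and physical-exam hypotheses share the problem of comparator, but no magnitude was calculated for them.

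The change is worth making because it is cheap and removes a known source of incomparability. It would not turn this feasibility trial into a confirmatory safety comparison.

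**What to change.** In Section 11.3.1, and in the SAP when written:

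- Name the concurrent fat-alone arm as the reference for all three hypotheses, and restate the null for each against the same arm.
- Report each ADRC arm, and the two pooled, minus fat alone, as the difference in the proportion of subjects with an event through Week 24, with 95% confidence intervals on the Safety set.
- Do this for all adverse events, for vital-sign and physical-exam abnormalities, and for the ADRC- or injection-related and Appendix B events that Section 11.3 already separates.
- Keep published fat-grafting rates as descriptive context, with source, event definition and follow-up stated.
- State that the comparison is for estimation, and that unblinded assessment remains a limitation.

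Cost: protocol and SAP wording and one additional table, with no new data. The downside is wide intervals, about 21 to 27 points either side for 40 v 20 and 25 to 31 for 20 v 20 at event rates of 20% to 55%, so the report will have to describe the safety comparison as imprecise.
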